9.5 CONFIDENTIALITY AND SECURITY OF DATA

The following measures will be taken in order to maintain confidentiality of any information obtained from or about the subjects:

Identifiable Information and Linking Lists/Files

- A de-identifier ID will be generated and assigned to each patient. The linking lists with de-identifier ID, name and Medical Record Number of the patient will be maintained separately from research data in RedCap. Access to the list/file will be limited to approved research personnel. The study data coded upon abstraction, and any direct identifiers, will be maintained separately from data
- Collection of sensitive information about subjects (PHI) is exclusively limited to the amount necessary to achieve the aims of the research study and no unneeded sensitive information will be collected
- Only the minimum health information pertaining to the study will be collected. This will include clinical, procedure, and disease-related factors affecting the study outcomes.

- Identifiable information will be destroyed as soon as possible after it is no longer needed for research purposes
- Identifiable information will not be used or disclosed for any purposes not described in this application

Research Records and Data Storage

- Electronic research records will be stored in shared network folder on Cedars-Sinai network (no storage on non-CSMC computer)
- All laptops used for collecting and storing research data or patient information will be encrypted in accordance with EIS standards. Laptops purchased with grant or other Cedars-Sinai funds will be processed through EIS to register and encrypt the laptop
- The data will only be made available to certified research personnel with IRB approval for access, through the use of passwords and encryption (No downloading to unencrypted portable devices, such as flash drive, personal laptop, etc.)
- Access will be only at Cedars-Sinai or through approved VPN access
- Hard copy research records will be stored in secure location (e.g. locked cabinet, office); Paper records with PHI will not be removed from Cedars-Sinai premises.

10.0 DATA AND SAFETY MONITORING

10.1 DATA MONITORING AND QUALITY ASSURANCE

Minimal Risk Monitoring

Adherence to the protocol, Good Clinical Practices (GCP), and institutional policy will be monitored by the PI during the course of the study through routine Disease Research Group (DRG) meetings (or equivalent). In addition, the SOCCI Cancer Clinical Trials Office (CCTO) Quality Management Core (QMC) will conduct focused internal monitoring visits and audits for data quality and protocol adherence. QMC reports will be forwarded to the SOCCI Data and Safety Monitoring Committee (DSMC). Refer to the DSMC Charter for more details. For any protocol, QMC has the authority to request more frequent reviews or focused safety monitoring if it is deemed appropriate for any reason.

10.2 SAFETY MONITORING

Minimal Risk Monitoring

Oversight of the progress and safety of the study will be provided by the PI. The PI will maintain continuous safety monitoring for the duration of the study by reviewing subject/study data. Adverse events and unanticipated problems are not expected, but if they occur, they will be documented and reported according to CS-IRB policies and procedures. If the PI becomes aware of any new safety information that may place subjects at increased risk than what was previously known, the IRB will be promptly notified and if warranted, enrollment may be held until the PI determines whether a modification to the study is necessary and/or the informed consent documents are updated accordingly. It is the responsibility of the principal investigator to adhere to the Data Safety Monitoring Plan throughout the life of the study.

In addition, this protocol will utilize the SOCCI Data and Safety Monitoring Committee will provide another layer of data and safety oversight. DSMC membership and responsibilities are governed by the committee charter. The annual DSMC findings and recommendations will be

reported in writing to the Principal Investigator as a summary letter which will be forwarded by the Principal Investigator or designee to the CS-IRB. The DSMC may increase or decrease the frequency of study review, at their discretion. Refer to the DSMC Charter for details of the DSMC review.

11.0 STATISTICAL CONSIDERATIONS

11.1 STUDY OUTCOME MEASURES

We have previously performed RNA-seq on 25 MIBCs, to identify 3 key bladder tumor cell populations that are differentially represented across tumors. These cells show major molecular differences and their proportions within a tumor are strong predictors of the aggressiveness of the disease, as measured by time to recurrence. Further, we have applied this data to develop a deconvolution algorithm that is able to predict their proportions in other tumors within TCGA based on bulk RNA-seq data. Now, we will apply this deconvolution algorithm to the RNA-seq data from 10 tumors in conjunction with imaging data to search for image and genomic parameters that predict tumor stage, outcomes and the presence of each of the cancer cell types, as well as fibroblasts and different immune infiltrates.

Querying a small population for numerous parameters can lead to high false positive rates, thus from our retrospective work, we will apply 30 radiomics parameters and no more than 40 genes in our network analyses, prioritization of genes and their interactions will be done using Lynx, PINTA and String algorithms to perform annotation, clustering, enrichment analysis, and prediction of high-confidence triggers and mediators in various cell populations of interest. Predictions of gene interactions and reconstruction of molecular pathways for the phenotypes of interest will be done using PINTA and STRING algorithms. These pipelines will be executed at scale using cloud resources. In addition to cloud resources, we will leverage the existing infrastructure available to the [name] lab. The results will be annotated with information from Lynx knowledge base integrating > 35 biological databases and publicly presented for revision and analysis via Web-based user interface developed in the course of the project. Biostatistical and bioinformatic comparisons of the molecular profiles with MRI imaging characteristics will be performed using a variety of publicly available and locally developed software applications.

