accurately stage patients (Fig. 1) leading to better medical decision making as it relates to BP techniques. Our central hypothesis is that a radiogenomic profile exists that a) is specifically associated with BCa and b) can be utilized to more effectively and accurately stage BCa. We seek to develop a computational algorithm that predicts, from radiographic imaging data and genetic alterations from RNA-seq data of a tumors, the relative proportions of predefined cancer cell populations, which lends to aggressiveness and BCa extent. To begin to test this hypothesis, we propose to conduct a pilot study of integrating radiomics data with genomics data in patients with localized MIBC and correlating to final pathology at the time of radical cystectomy. By improving our ability to better stage patients with MIBC, this work could facilitate future studies to explore a radiogenomic signature associated with MIBC and improve patient outcomes.

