Urine sample(s) will be obtained by asking the patient to provide urine into a provided container or via urinary catheter placed at the time of surgery. Approximately 50 mL will be obtained, centrifuged, separated into cellular pellet and supernatant and stored at -80^0 C, in a secure biorepository freezer in CSMC BioBank.

(3) Tissue Specimens:

A fresh frozen tissue sample from TURBT and subsequent cystectomy specimens will be obtained by CSMC BioBank personnel. The tissue samples will be snap-frozen in liquid nitrogen and stored in -80^0 C freezers in CSMC BioBank. When needed for analysis, BioBank will send a portion of the de-identified TURBT tumor (5mm^3) to CS Genomic Core for RNA extraction, and RNA-seq.

Or FFPE tissue sample from a TURBT will be requested. Specifically we will request 1 H&E from the FFPE block with tumor as well as 10 unstained slides.

Using standard techniques, CS Genomic Core will perform RNA-seq. Biostatisticians and Bio-informaticians will assess correlations between radiomics, genomics and pathology data.

Table 8 Correlative Studies timing and requirements

Specimen	Quantity	MRI	TURBT	Cystectomy
Whole Blood ACD tube	1x15 mL+		X+	X+
Urine	50 mL		X+	X+

Bladder tissue (Fresh)	~5mm ³		X~	X+
Bladder tissue (FFPE)	1 H&E 10 unstained		X~	

~, used for sequencing

+, banked in Cedars' Biobank for future use

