9.2 VARIABLES COLLECTED

The following data points/variables will be collected:

1. RNA-seq of bladder tumor
2. Imaging Measurement Tools:
 - MRI Pelvis protocol with modified sequences
 - T1 and T2 imaging (relaxation differences between tumor/tissue)
 - 3D imaging of abdomen (w/o contrast)
 - DWI multi-b value (cellularity, density)
 - 3D imaging of abdomen (w/o contrast)
 - ADC maps for slow and fast diffusion components
 - DCE-MRI (microvascular density, vascularity, vascular permeability)
 - 3D imaging of abdomen (w/ contrast)
 - Kinetic parameter maps, K^{trans} , k_{ep} , v_e , AUC
 - Fractional blood volume, v_p

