11.2 SAMPLE SIZE CONSIDERATIONS

The main hypothesis to be tested is whether there is association between radiogenomic features and pathologic stage. The prospective study is a pilot study to: a) generate high quality data and b) show feasibility, which we will define as know-how to create a radiogenomic workflow and to learn about the correlation structure of the radiogenomics parameters of interest, which will allow us to design future studies with adequate power. Pearson's Correlation hypothesis tests with 5% significance level (two-sided) and 80% power allows sample sizes of 10 patients to detect a difference between the null hypothesis correlation of zero and the alternative hypothesis correlation of 0.76 (23). In addition, sensitivity and specificity of several potential predictors will be estimated. The maximum width of the 95% confidence interval for proportions (sensitivities or specificities) associated with sample sizes of 10 patients are 0.63 (24). We anticipate 50% of subjects presumed to have MIBC at the time of TURBT and/or presumed not to have metastatic disease to not complete the study, i.e., undergo radical cystectomy, which will denote true pathologic stage. Thus, our final sample size to enroll is 20.

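### Section 11.1 lets genes predict cell types that are calculated from the same RNA-seq, so for genes used by the deconvolution algorithm the association is partly built in

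*Combined protocol and SAP*

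**What the plan says.** Section 11.1 reports earlier RNA-seq work on 25 tumors that identified 3 tumor cell populations and was used to "develop a deconvolution algorithm that is able to predict their proportions in other tumors within TCGA based on bulk RNA-seq data". For this study, "we will apply this deconvolution algorithm to the RNA-seq data from 10 tumors in conjunction with imaging data". The same sentence gives the purpose: "to search for image and genomic parameters that predict tumor stage, outcomes and the presence of each of the cancer cell types", and adds fibroblasts and immune infiltrates as further targets. Section 1.0 states a similar aim, an algorithm that "predicts, from radiographic imaging data and genetic alterations from RNA-seq data of a tumors, the relative proportions of predefined cancer cell populations".

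The candidate list is capped: "we will apply 30 radiomics parameters and no more than 40 genes in our network analyses". It is said to come from the group's retrospective work.

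The molecular data are a single assay. Section 9.2 lists "RNA-seq of bladder tumor" and no other molecular variable. Section 4.0 says "Using standard techniques, CS Genomic Core will perform RNA-seq". Table 8 marks only TURBT tissue for sequencing and marks cystectomy tissue for banking.

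**The concern.** A deconvolved proportion is a function of the expression values fed into the algorithm. If one of those genes is then tested as a predictor of that proportion, the same measured value, noise included, sits on both sides of the test. A chance high reading for a marker gene raises the estimated share of its cell type, and the two then correlate even if the true share is the same in every tumor.

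An independent measure of composition would break the loop, but none is planned. Single-cell sequencing appears only as background and earlier work (Section 1.0). The pathology data to be extracted are histology, grade and stage (Section 9.1). The H&E slide requested with outside specimens has no planned reading of cell composition. No rule keeps the deconvolution genes out of the candidate list. The cap on features addresses multiplicity, which is a different problem.

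The objective (Section 2.0) is to learn a correlation structure that will inform the power of later studies. A gene-to-cell-type correlation that is partly an artefact could be carried forward as a finding.

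**Working it through.** **1. The plan's own figures.** Section 11.2 uses "5% significance level (two-sided) and 80% power allows sample sizes of 10 patients" to detect a correlation of 0.76. The critical value is |r| = t/√(n − 2 + t²) with t = 2.306 on 8 degrees of freedom, so 2.306/√(8 + 5.318) = 0.632. Simulated power at a true correlation of 0.76 is 79.8%, which reproduces 80%. The maximum exact (Clopper-Pearson) 95% interval width at n = 10 is 0.626, which reproduces 0.63. Enrolment is 10/(1 − 0.5) = 20. None of these figures depends on the point at issue.

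**2. Which parts of the search share a measurement.**

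| Predictor | Target | Source of predictor | Source of target | Shared? |
|---|---|---|---|---|
| Imaging | Cell type | MRI | RNA-seq | No |
| Imaging | Stage, outcome | MRI | Pathology, follow-up | No |
| Genes | Stage, outcome | RNA-seq | Pathology, follow-up | No |
| Genes | Cell type | RNA-seq | Same RNA-seq | Yes, for genes the algorithm uses |

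Only the last row is circular.

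**3. A simple bound on the mechanism.** Suppose a cell-type score is the mean of k independent, equally variable genes. The correlation of any one of them with the score is 1/√k, although nothing biological links them. The chance of |r| > 0.632 at n = 10 is then:

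- k = 5: 1/√5 = 0.447, 26%
- k = 10: 1/√10 = 0.316, 14%
- k = 20: 1/√20 = 0.224, 9%
- k = 40: 1/√40 = 0.158, 7%

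**4. The same with a deconvolution step.** Assumed inputs, none from the documents except n = 10, the 5% level and the 3 populations: each signature gene is a 5-fold marker of one type; gene noise is log-normal with SD 0.5 on the log scale; proportions are estimated by non-negative least squares (NNLS) and scaled to sum to 1; true composition is identical in all tumors. Any association with a cell type is then artefact or chance.

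| Signature genes | Signature gene vs own cell type, share with \|r\| > 0.632 | Independent gene outside the signature |
|---|---|---|
| 12 | 23% | 5% |
| 30 | 11% | 5% |
| 40 | 10% | 5% |
| 90 | 7% | 5% |

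**5. When tumors do differ in composition.** Marker genes then truly track their cell type, so the fair comparator is the same gene against the true proportion. With composition drawn from a Dirichlet(5) distribution, and log-SD 0.3 / 0.5:

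| Signature genes | Against estimated proportions | Against true proportions | Difference, points |
|---|---|---|---|
| 12 | 53% / 34% | 40% / 19% | 13 / 15 |
| 40 | 43% / 23% | 40% / 19% | 3 / 4 |
| 99 | 41% / 20% | 41% / 18% | 0 / 2 |

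Most of the raw rate is genuine signal unless the signature is small.

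**The case against.** The strongest reply is that the wording is compressed and can be read harmlessly: RNA-seq gives the proportions, imaging is related to them, and both are related to stage and outcome. The aim in Section 1.0 can likewise be read as a plain description of deconvolution, and the phrase about genomic parameters could mean the deconvolved proportions themselves. Section 11.1 also closes on comparing molecular profiles with MRI characteristics, which is not circular. This shows that a harmless reading exists. It does not remove the point, because Section 11.1 names genomic parameters as predictors and cell types as a target in one sentence, and nothing restricts which genes enter.

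It is also fair that the effect is small with a large signature, and that this is one exploratory part of a 10-patient feasibility pilot with no decision tied to it. That stands, and it sets the severity.

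Three stronger readings are tempting, and the documents do not support them:

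- A reader might infer that only the imaging side of the cell-type search is informative. Genes outside the signature are not circular, and in the simulation independent genes of that kind stay at 5%. They do share a sample and library with the target, hence possible common technical variation, which is a reason for a descriptive label.
- A reader might infer that built-in gene associations would displace imaging in a joint model. Section 1.0 mentions both inputs, but Sections 11.1 and 11.2 specify no combined image-plus-gene model of cell type.
- A reader might take the high hit rates under varying composition as the size of the artefact. Step 5 shows that most of them are real signal.

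**Conclusion.** The point holds, within limits. As written, the gene-to-cell-type part of the search in Section 11.1 is partly circular for any gene the deconvolution algorithm uses, because no other source of cell composition is planned and no rule excludes those genes.

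Its size in this trial cannot be calculated. The documents do not give the signature, its length, the type of algorithm, or its overlap with the candidate genes. Both the list and the algorithm come from the group's earlier work, so overlap is plausible, but it is not stated. Under the assumptions of step 4, the false-positive rate for signature genes runs from about 7% (90 to 100 genes) to 23% (12 genes), against the nominal 5%.

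The main hypothesis on pathologic stage, the sample size, the imaging-to-cell-type search, and the prediction of stage and outcomes are not affected. This is a cheap improvement of low severity.

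**What to change.** In Section 11.1, state that the deconvolved cell-type proportions are targets for the imaging parameters. Keep the prediction of stage and outcomes from image and genomic parameters as planned. If gene-to-cell-type associations are also to be reported, remove the genes used by the deconvolution algorithm from the candidate list for that analysis and label the result descriptive. Align the sentence on the computational algorithm in Section 1.0 with this.

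The cost is a change of wording and one gene-list filter, which the investigators can apply because the algorithm is their own. It needs no new patients, samples or assays. The downside is fewer gene-to-cell-type associations to report.

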Clinical Research Protocol

Study Title: Radiogenomics of muscle invasive bladder cancer

Protocol Number:	IIT2020-22-[name]-Radiogenomics
Current Version Number:	1.2
Current Version Date:	12 July 2022
Investigational Product:	N/A
IDE Number:	N/A
NCT Number:	NCT04806334
Development Phase:	Pilot
Funding Organization:	Cedars-Sinai
Principal Investigator:	Name: [name], MBA [contact] [contact] E-mail: [contact]
Clinical Site:	Cedars Sinai Medical Center [name]

TABLE OF CONTENTS

PROTOCOL SUMMARY	3
1.0 BACKGROUND, RATIONALE.....	4
2.0 STUDY OBJECTIVES.....	6
3.0 STUDY POPULATION	6
3.1 SELECTION OF THE STUDY POPULATION.....	6
3.2 INCLUSION CRITERIA.....	7
3.3 SUBJECT SCREENING AND ENROLLMENT.....	8
4.0 STUDY DESIGN AND METHODS.....	8
5.0 CLINICAL ASSESSMENT.....	10
6.0 ADVERSE EVENT REPORTING AND DOCUMENTATION.....	11
7.0 DISCONTINUATION AND REPLACEMENT OF SUBJECTS.....	15
8.0 SCHEDULE OF PROCEDURES.....	16
9.0 DATA COLLECTION AND MANAGEMENT	117
10.0 DATA AND SAFETY MONITORING	118
11.0 STATISTICAL CONSIDERATIONS.....	119
12.0 REFERENCES.....	20

PROTOCOL SUMMARY

Title:	Radiogenomics of muscle invasive bladder cancer
Protocol number:	IIT2020-22-[name]-Radiogenomics
Phase:	Pilot
Study Design:	Single center clinical trial evaluating identifying a distinct radiogenomic signature of muscle invasive bladder cancer (MIBC)
Study Duration:	84 weeks
Objective:	Primary Objective: To show feasibility, which we will define as know-how to create a radiogenomic workflow and to learn about the correlation structure between the radiomic and genomic parameters of interest, which will allow us to design future studies with adequate power.
Number of subjects:	20 subjects
Main Inclusion criteria:	Adults with sessile bladder masses, suspected of harboring MIBC
Study product, dose, route of administration:	N/A
Statistical Analysis:	We will apply a deconvolution algorithm to the genomic data from patients with MIBC in conjunction with magnetic resonance imaging (MRI) data to search for genomic and radiomic parameters that predict tumor stage and outcomes.

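### The cap of 30 radiomic parameters and 40 genes sets no family-level error rate, and the 80% power at r = 0.76 is a per-test figure that does not hold for a given feature once error is controlled across the search

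*Combined protocol and SAP*

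**What the plan says.** Section 11.1 states the hazard itself: "Querying a small population for numerous parameters can lead to high false positive rates". Its response is that "from our retrospective work, we will apply 30 radiomics parameters and no more than 40 genes in our network analyses", with genes and their interactions prioritised by Lynx, PINTA and STRING.

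The work is described as a "search for image and genomic parameters that predict tumor stage, outcomes and the presence of each of the cancer cell types", and fibroblasts and immune infiltrates are added as further targets. The Protocol Summary likewise plans "to search for genomic and radiomic parameters that predict tumor stage and outcomes", and section 4.0 (Correlative studies) says "Biostatisticians and Bio-informaticians will assess correlations between radiomics, genomics and pathology data".

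Section 11.2 then announces a test: "The main hypothesis to be tested is whether there is association between radiogenomic features and pathologic stage". It supports the sample size with Pearson correlation "hypothesis tests with 5% significance level (two-sided) and 80% power allows sample sizes of 10 patients to detect a difference" between zero and 0.76. The same section calls the study a pilot for learning the correlation structure, "which will allow us to design future studies with adequate power".

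The document does not name a primary feature, list the 30 and 40 candidates, say how many feature-versus-stage tests will be run, or give a family-wise or false-discovery target.

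**The concern.** The plan identifies a multiplicity problem and offers a remedy that does not control it. Limiting the candidates lowers the number of chance findings. Choosing them from retrospective work makes them more plausible. Neither says how often the search will produce a false lead in these 10 patients.

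Section 11.2 puts a 5% level and 80% power beside a hypothesis about features in the plural. A reader can take the pair to describe the whole search, but it describes each test taken alone.

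Two things are at stake. First, some nominally significant features are to be expected by chance, and the plan has no rule for grading them. Second, the results are meant to inform the size of later studies. If correlations are carried forward because they reached significance, they will tend to be too large.

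**Working it through.** **Inputs.** From section 11.2: n = 10, two-sided 5%, r = 0 against r = 0.76. From section 11.1: 30 radiomic parameters and at most 40 genes. Assumed, because the document does not say: m, the number of tests in the family. The values shown are 5, 10, 30, 70 (30 + 40) and 1,200 (30 × 40 radiomic-gene pairs).

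**1. The plan's own figure.** The critical correlation is r_c = t / √(n − 2 + t²), with t the two-sided 5% point on 8 degrees of freedom (2.306). So r_c = 2.306 / √(8 + 5.318) = 0.632. Integrating the exact bivariate-normal density of the sample correlation beyond ±0.632 at a true r of 0.76 gives power 79.8%, and the correlation detectable at 80% power is 0.761. A simulation of 400,000 samples gave 79.7%. The stated figure reproduces.

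**2. The same figure in an unadjusted search.** The distribution of one feature's r does not depend on how many other features are tested. At an unadjusted 5%, each feature with true r = 0.76 therefore keeps about 80% power.

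**3. False positives in that search.** If no feature is related to stage, the expected number of false positives is 0.05 × m, whatever the correlation among features. If the tests are independent, the chance of at least one is 1 − 0.95^m.

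**4. Power for a given feature under Bonferroni.** Step 1 is repeated at a level of 0.05/m, n = 10, true r = 0.76.

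| Tests m | Expected false positives, unadjusted | Chance of at least one, independent | Critical r, Bonferroni | Power at 0.76, Bonferroni | Detectable r at 80% power |
|---|---|---|---|---|---|
| 1 | 0.05 | 5% | 0.632 | 80% | 0.76 |
| 5 | 0.25 | 23% | 0.765 | 54% | 0.85 |
| 10 | 0.5 | 40% | 0.805 | 43% | 0.88 |
| 30 | 1.5 | 78.5% | 0.854 | 27% | 0.91 |
| 70 | 3.5 | 97% | 0.883 | 17% | 0.93 |
| 1,200 | 60 | about 100% | 0.943 | 3% | 0.96 |

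**5. Effect of correlated features.** Radiomic features and genes are unlikely to be independent. Null features were simulated in sets of 30 and 40, equally correlated within each set (20,000 replicates). The chance of at least one false positive over 70 was 97, 83, 52 and 37% at within-set correlation 0, 0.5, 0.8 and 0.9. The expected count stays at 3.5.

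**6. Precision and selection.** For an observed r of 0.76 at n = 10, Fisher's z is 0.996 with standard error 1/√7 = 0.378. The limits are 0.996 ± 1.96 × 0.378, or 0.255 and 1.737, which transform back to 0.25 and 0.94. A correlation must reach 0.632 in absolute value to be significant. At a true 0.76, those that pass average 0.81.

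**The case against.** The strongest reply is that the power statement is not wrong. Section 11.2 speaks of tests at a 5% level, and each truly associated feature has about 80% power at that level, named in advance or not. This stands. A reader might infer that the 80% holds only for one pre-specified feature, or that power falls simply because many features are searched. The document does not support either inference. Power for a given feature falls only when error is controlled across the family. The chance of finding at least one true feature is a different quantity, and it rises with the number of true features.

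A second reply is that the family is inferred. The 30/40 limit is written for the network analyses, and nowhere are 70 feature-versus-stage tests promised. The Pearson sentence closely follows the remark on correlation structure, so it might even refer to radiomic-gene pairs. This also stands, and it is why a range of m is shown. Even 5 independent tests give a 23% chance of a false lead.

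A third reply is that this is a pilot aimed at feasibility, and the document does not say that correlations will be carried forward because they were significant. At the planning value the inflation is about 0.05 (0.81 against 0.76). This limits the harm. It does not remove the need for a reading rule, because section 11.2 announces a main hypothesis with a level and a power.

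Finally, Bonferroni is stricter than a permutation or false-discovery method when features are correlated. It is used here only as a bound.

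**Conclusion.** The point holds in this form. The cap and the prioritisation leave the family-level error rate unset, and the per-test 5% in section 11.2 is the only error rate given. It would be too strong to say that the plan has no error rate at all.

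The 80% at r = 0.76 is correct per test, but it cannot be had for a given feature together with 5% error over the search. Under Bonferroni over 5 to 70 tests it falls to between 54% and 17%, and over 1,200 radiomic-gene pairs to about 3%. Left unadjusted over 70 null features, the search yields 3.5 false positives on average. The chance of at least one runs from 97% with uncorrelated features to about 37% at within-set correlation 0.9.

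These sizes rest on assumed values of m, an assumed correlation structure and a normally distributed stage score, whereas pathologic stage is ordinal. A reader might also conclude that the pilot is too small and must enrol more. That does not follow, because its aim is feasibility and low power is not itself the fault. The change is moderate, confined to analysis and wording, and should be made.

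**What to change.** 1. In section 11.1, choose one of two routes. Either name one primary feature-versus-stage test and label everything else exploratory, or list the feature-versus-stage tests as one family and control it. Suitable controls are a permutation test on the largest absolute correlation (permuting stage across patients) or Benjamini-Hochberg at a stated level. In both cases label the radiomic-gene, outcome and cell-type searches exploratory.
2. In section 11.2, add: *The 80% power at r = 0.76 is per test at an unadjusted two-sided 5% level; it does not hold for a given feature under family-wise or false-discovery control over the feature set.* The Bonferroni figures may be added as a conservative bound, with their assumptions.
3. Report correlations with 95% confidence intervals. Do not size later studies on correlations selected for significance without allowing for that selection.
4. If predictors or cut-offs are chosen in the same 10 patients, label their sensitivity and specificity as apparent, meaning optimistic.

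The cost is a few sentences and a short script on data already being collected, with no new patients, visits or assays. The downside is that fewer results will be called significant and the stated power will read less favourably.
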